8.3.8 EVENTS OF SPECIAL INTEREST

Not applicable.

8.3.9 REPORTING OF PREGNANCY

Not applicable.

8.4 UNANTICIPATED PROBLEMS

8.4.1 DEFINITION OF UNANTICIPATED PROBLEMS (UPIRTSOS)

Unanticipated problems (UPs or UPIRTSOS) involving risks to participants or others include, in general, any incident, experience, or outcome that meets all of the following criteria:

- Unexpected in terms of nature, severity, or frequency given (a) the research procedures that are described in the protocol-related documents, such as the Institutional Review Board (IRB)-approved research protocol and informed consent document; and (b) the characteristics of the participant population being studied;
- Related or possibly related to participation in the research (“possibly related” means there is a reasonable possibility that the incident, experience, or outcome may have been caused by the procedures involved in the research); and
- Suggests that the research places participants or others at a greater risk of harm (including physical, psychological, economic, or social harm) than was previously known or recognized.

8.4.2 UNANTICIPATED PROBLEM REPORTING

The investigator will report UPS (UPIRTSOS) – and potential UPIRTSOS - to the DCOC (who will in turn report to the reviewing IRB when the reviewing IRB is UAMS) and the local IRB as well as any other persons or groups noted in the DSMB charter. Reports to NIH and the DSMB will be made by following the chain of notification.

These problems must be reported to the reviewing/local IRBs according to the reviewing/local IRB's contemporaneous policies and procedures.

For most sites involved in the study, the reviewing IRB will be the University of Arkansas for Medical Sciences (UAMS) IRB. The UAMS IRB contemporaneous policy, 10.2., *Events that must be reported to the IRB and IRB Actions* (effective July 6, 2020) is available via <https://irb.uams.edu/irb-policies/current-irb-policies/>

As of the writing of this section of the protocol (03/23/2022), UAMS IRB reporting requirement per policy 10.2 are:

UPIRTSO Reporting Requirement	
Unanticipated Problem	Required Reporting Time to UAMS IRB
Death or life-threatening	Immediately to IRB office or IRB Chair
All other events	Within 10 days of event or notification of event if non-local

Reports typically require the following information:

- Protocol identifying information: protocol title and number, PI's name, and the IRB project number
- Event date
- Event location
- Nature of the risk
- How the risk relates to research
- A detailed description of the event, incident, experience, or outcome
- A description of any changes to the protocol or other corrective actions that have been taken or are proposed in response to the UP

Examples of UPs/UPIRTSOS that are not an AE or SAE, but which would need to be reported include:

- Breach of confidentiality
- Manufacturer recall of equipment used in the protocol

8.4.3 REPORTING UNANTICIPATED PROBLEMS TO PARTICIPANTS

The parent(s)/guardian(s) of participants will be notified of those study-related (or potentially study-related) SAEs or UPs that may affect either the parent(s)/guardian(s) willingness to allow their child to continue with the study or the future health of the participant. This determination can be made by any of the following: the IRB, the medical monitor, the DSMB, the DCOC, or the NIH. The person or oversight body that makes the determination will inform the DCOC, which will instruct the site PIs/study coordinators to contact those participants enrolled through their site. Contacts with parent(s)/guardian(s) of participants, if necessary, will be recorded on the appropriate CRF and/or study log.

9 STATISTICAL CONSIDERATIONS

9.1 STATISTICAL HYPOTHESES

Primary Objective: To test the efficacy of a HEPA filtration unit home intervention, relative to the control arm, with respect to respiratory symptom burden (as measured by symptom-free days; SFD) over 24 weeks following activation of filtration.

Primary Endpoint: Number of caregiver-reported SFDs over 24 weeks following activation of filtration (SFD defined as a 24-hour period without coughing, wheezing, or trouble breathing)

Statistical Hypothesis: Mean of SFDs in the HEPA filtration home intervention group is larger than mean of SFDs in the control group.

Secondary Objective 1: To test the efficacy of a HEPA filtration home intervention, relative to the control arm, on the number of unscheduled healthcare visits for respiratory symptoms over 24 weeks following activation of filtration.

Secondary Endpoint 1: Caregiver reported counts of unscheduled healthcare visits from each of the metrics including hospitalizations, Emergency Department (ED) visits, Urgent Care (UC) visits, and other unscheduled medical visits for respiratory complaints (cough, wheeze, or trouble breathing). A sum of counts (or total counts) of all metrics is also used as the secondary endpoint.

Statistical Hypothesis 1: Mean of counts of unscheduled healthcare visits for respiratory symptoms in the intervention group is smaller than mean of counts of unscheduled healthcare visits for respiratory symptoms in the control group.

Secondary Objective 2: To test the efficacy of HEPA filtration home intervention, relative to the control arm, on difference in QOL.

Secondary Endpoint 2: Total QOL score, as measured by the PedsQL™ Pediatric Quality of Life Inventory Infants Scales questionnaire at the end of the intervention period.

Hypothesis 2: Child QOL will be higher in families that receive the HEPA intervention compared to controls.

Secondary Objective 3: To test the efficacy of HEPA filtration home intervention, relative to the control arm, on PM_{2.5} levels in the home over 24 weeks following activation of filtration.

Secondary Endpoint 3: Weekly average PM_{2.5} levels as measured by 2 in-home PurpleAir monitors over 24 weeks and scaled to the unit of $\mu\text{g}/\text{m}^3$ per week.

Hypothesis 3: Mean of PM_{2.5} level in the intervention group is lower than mean of PM_{2.5} level in the control group.

9.2 SAMPLE SIZE DETERMINATION

Sample Size Justification:

We plan to enroll (consent) up to 228 participants.

To account for an anticipated attrition rate of 16% per arm, the power analysis is based upon a sample size of 196 participants, or 98 participants per arm. From a similar previously published study, it was found the mean of days with symptoms was 70 days (equivalently the mean of SFDs was 98 days out of total 24 weeks or 168 days of observation), and the standard deviation was 43 days.⁵ The proposed sample size will provide 90% power to detect an effect size of 0.465, or a difference of 20 symptom-free days with a standard deviation of 43 days, using a two sample t-test.

Randomization Scheme:

The randomization will be stratified by site. Within each site, participants will be randomized in a 1:1 allocation to receive active HEPA filtration (intervention group) and inactive HEPA unit (control group). Permuted block randomization will be employed.

9.3 POPULATIONS FOR ANALYSES

Analysis Population:

Intent-to-Treat (ITT) Population: The ITT population will include all participants who are randomized to either HEPA filtration (intervention group) or inactive filter unit (control group) (referred to as two groups in the analysis section).

Per-protocol (PP) Population: The PP population will include all participants who are randomized to either the HEPA filter (intervention group) or inactive filter (control group) and have used HEPA unit on average for both units >80% of the time.

The primary set of analyses for this study will be based on ITT population. A separate analysis will be done with the PP population.

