Experimental condition, Active HEPA filtration unit use: The intervention group will use two Winix 5500-2 HEPA filtration units (Appendix A) (<https://winixamerica.com/product/5500-2/>). One will be placed in the child's sleep space and one will be placed in another common room with both units running continuously on the "high" (i.e., level 3 / second from highest) setting. Each unit is 8.2 x 15.0 x 23.6 inches, and verified for a 360 sq. foot room. If a home is too small to accommodate 2 Winix units (for example, a single room residence'), one Winix unit may be used for the study. Additional features beyond HEPA and carbon filter, include plasmawave technology to reduce volatile organic compounds and odors. The plasmawave feature will be turned off to avoid ozone production.

Control condition, Inactive filter unit use: The control group will use identical-appearing Winix 5500-2 units and similar setup procedures as described above, but with no HEPA or carbon filters.

The manufacturer indicates that HEPA filters can last up to 12 months. For this reason, the filters will not be changed during the 24-week intervention period. Changeout of filters also adds the additional risk of unintentional unmasking of the family or research team members. Ideally, the carbon filter in the HEPA unit is cleaned every 3 months. However, since reduction of pollutants (e.g., volatile organic compounds) addressed by the carbon filter are not targets of the intervention, the carbon filters will not be changed out during the 24-week study.

If a HEPA unit or control unit breaks, malfunctions, or stops working, the entire unit needs to be replaced by the study team as soon as possible (by mail, pickup, or delivery). While awaiting replacement, the family will be instructed to use the working HEPA unit in the room where the infant spends the most hours.

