6.2.4 PREPARATION

Education of parent(s)/guardian(s) of participants regarding equipment use will occur during the child's hospitalization and then remotely (video, phone, or other family-preferred communication means) post-discharge to home. All participants will receive:

- 2 HEPA or control units (unless home is small enough that only one HEPA unit is needed),
- 2 kW meters (0 kW meters if home has only two-prong outlets),
- 2 PurpleAir monitors (1 if home using only one HEPA unit) and mobile hotspot with power adapter,
- 4 power strips or similar,
- 1 tape measure,
- Basic education on strategies to improve indoor air quality, and
- 1 Healthy Homes Kit.

The local site research team will assist participants remotely with setup of all study equipment.

Study staff will ensure correct placement and setup of the PurpleAir monitors and hotspot, HEPA/control units, and kW meter following a checklist (submitted separately or will be included or referenced in MOP).

Because parent(s)/guardian(s) of participants can set up all study equipment with remote support, the study team should not need to enter any participant's home. However, to reduce barriers to participation, study staff will be permitted to assist any parent(s)/guardian(s) of participant's in their home if all remote options for technical assistance are exhausted, and it is necessary to troubleshoot problems in person.

To facilitate the inclusion of rural children, this protocol allows for providing study equipment at hospital discharge to home, mailing equipment, or locally arranged pickup/delivery, and remote study activities. There are no required in-person study visits.

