- **Healthcare visits:** The parent/guardian will record the number of hospitalizations, ED/UC visits, and other medical visits for respiratory symptoms. This will be a (Y/N) for whether they participant (child) had a healthcare visit in the past week. If Y, there will be a prompt to enter the number of visits for each visit type. If N, they will move on to the next section, "Time away from home."
- **Time Away from home:**
 - **Days away from home:** The parent/guardian will be prompted to enter how many days that week the child spent more than 6 hours outside the home (0-7 days).
 - **Nights away from home:** The parent/guardian will be prompted to enter how many nights that week the child spent away from their primary residence (away for vacation, staying with someone else, etc.) (0-7 days).
- **Equipment use:**
 - **HEPA/control unit use:** For each room with a HEPA/control unit, the parent/guardian will be asked to respond Yes/No to whether they used unit and asked to report the usual setting used (1, 2, 3, or 4). If applicable, the parent(s)/guardian(s) will also record the numerical reading visible on the kW meter attached to each HEPA/control unit. This will be a simple entry of the numbers displayed on the kW meter to respond to the survey prompt.
 - **PurpleAir monitor:** The parent/guardian will be asked whether the monitor is plugged in with the light on (Yes or No). They will also be asked whether the hot spot is on with bar light and 3 lighted dots on (Yes or No).

Quality of Life:

- The PedsQL™ Pediatric Quality of Life Inventory Infant Scales⁹⁸ questionnaire will be administered to a parent/guardian at the end of the intervention period. This is a validated outcome measure of QOL for infants 1-12 months (36 items) and 13-24 months (45 items). The constructs include 5 subdomains: physical functioning, physical symptoms, emotional functioning, and cognitive functioning.

The questionnaire will be administered online. The alternative will be for the research coordinator to obtain responses verbally.

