### 3.7. Study Adherence

Intervention compliance will be assessed in two ways: caregiver-reported HEPA/control unit use and through kW meters. Participants who have used HEPA/control unit on both units >80% of the time (at least 19 weeks out of 24 weeks) with recommended setting (running continuously on the level 3/second from the highest) will be considered as good adherence. Since compliance data may be incomplete, additional analyses will define adherence as >80% use for weeks with available compliance information.

- Families will be instructed to place kW meters on the units at the onset of installation within the home to assess usage compliance with HEPA/control units. These meters enable assessment of power consumption and estimate corresponding costs for energy usage. Increasing kWh over the course of participation will indicate HEPA/control unit use. When available, we will also quantify actual kWh usage during the intervention period by comparing observed kWh

used to the usage predicted from laboratory tests. The observed kWh used will be divided by the predicted usage and this quantity multiplied by 100 to determine adherence.

- Weekly surveys will also include prompts for parent(s)/guardian(s) to report whether they used the HEPA/control unit that week and on what setting it was most commonly used. The survey questions include the usage of the air unit for each room during the last full week (Sunday through Saturday), whether there is a red glow, and what is the usual setting on the air unit.

Note that the kW meters require three-prong electrical outlets. If a home has only two-prong outlets, they will not use the kW meter. Since not all participants will have kW meters and since power interruptions will change kW meter settings, caregiver reported HEPA/control unit use on weekly surveys will be the primary measure of compliance.

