### **4.2. Per-Protocol Population**

Per-protocol (PP) Population: The PP population will include all participants who are randomized to either the HEPA filter (intervention group) or inactive filter (control group) and have used HEPA/control unit on both units >80% of the time with recommended setting (running continuously on the level 3/second from the highest). Intervention compliance will be assessed primarily by caregiver-reported HEPA/control unit use as well as kW meters as described in section 3.7.

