## Statistical Analysis Plan

Protocol Number: 274137

	
Data related to PM2.5 will be generated from two PurpleAir monitors installed in each participating home in most cases. Some smaller homes will have only one PurpleAir monitor installed. The data will be collected by a research team (third party) at the University of Montana (UM) every day during the study or follow-up period for a total of 26 weeks (24 weeks after intervention). The UM team will then convert the original data into PM2.5 levels using an EPA-defined formula, after data cleaning, quality assurance (QA) and quality control (QC). The UM team has developed a protocol of procedures for downloading, QA/QC checking, cleaning, computing, and saving PurpleAir data to ensure high quality PM2.5 measurements. An R script has been developed, tested and saved in a server of the CPHR at UM.

Study Variables 

➤ Demographic characteristics

➤ Environmental factors

➤ Medical history

	
Description
 

➤ Please see Table 2 in section 6.4 for variable information.

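### The protocol and SAP define the per-protocol set differently, the SAP's 19-week rule misses its own 80% threshold, and one-unit homes and meter readings have no rule

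*Protocol*

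**What the plan says.** Protocol 9.3 makes intention-to-treat the primary analysis set and plans a separate per-protocol analysis of randomised participants who "have used HEPA unit on average for both units >80% of the time". It attaches no fan setting to that rule and does not say how time is counted.

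SAP 4.2 requires that participants "have used HEPA/control unit on both units >80% of the time with recommended setting", the setting being level 3. It says compliance is assessed mainly by caregiver report, with kW meters also used, and refers to SAP 3.7. There, good adherence on both units is translated as "at least 19 weeks out of 24 weeks) with recommended setting". Because compliance data may be incomplete, SAP 3.7 adds that "additional analyses will define adherence as >80% use for weeks with available compliance information".

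Three other places bear on the definition:

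- **Homes with one unit.** Protocol 6.1.1 says that in a home too small for two, "one Winix unit may be used for the study". The equipment list in Protocol 6.2.4 agrees: "2 HEPA or control units (unless home is small enough that only one HEPA unit is needed". SAP section 5 acknowledges small homes, but only for the air monitors: "Some smaller homes will have only one PurpleAir monitor installed".
- **The survey item.** Under Protocol 8.1, for each room with a unit, "the parent/guardian will be asked to respond Yes/No to whether they used unit", and then to give the usual setting. Protocol 6.4 and SAP 3.7 make this report the primary measure of compliance.
- **The meters.** The same two sections plan a kWh adherence percentage, observed over predicted use, where readings are available.

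SAP section 7 calls for any change from the protocol's statistical approach to be described there with its justification. It lists none.

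**The concern.** A per-protocol set should be fixed by a rule that two analysts would apply identically without seeing outcomes. Here the averaging rule differs between the documents, the setting condition appears in only one, and the SAP's week count disagrees with its own percentage. Neither document classifies a one-unit home. The threshold is worded as a share of time, while the main data source records only whether a unit was used at all in a week.

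What is at stake is the one named analysis of homes that used the units as intended. Protocol 5.2 describes the trial as an efficacy study under ideal circumstances, so readers will look at that analysis. Protocol 5.5 also notes that in some earlier studies families turned units off or ran them below the recommended setting, so partial use is a foreseeable problem. If these choices stay open, membership may be settled after results are known.

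**Working it through.** **Inputs.** Threshold: more than 80% (Protocol 9.3; SAP 3.7 and 4.2). Intervention: 24 weeks. SAP week count: at least 19 (SAP 3.7). Survey item: used or not used in each room, plus usual setting (Protocol 8.1).

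**1. The plan's own conversion.** 0.80 × 24 = 19.2 weeks.

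- 19/24 = 79.2%, which fails both a more-than-80% and an at-least-80% reading.
- 20/24 = 83.3%, the first whole week that passes.

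The SAP's figure of 19 weeks is therefore not reproduced.

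**2. The two rules on the same homes.** The protocol gives no conversion from time to weeks. As an assumption, use is counted here in weeks of reported use, as the SAP does. Protocol score = (weeks A + weeks B)/48. The SAP tests each unit separately out of 24.

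| Unit A | Unit B | Usual setting | Protocol 9.3 | SAP 3.7 and 4.2 |
|---|---|---|---|---|
| 24 | 16 | 3 | 40/48 = 83.3%, in | B = 66.7%, out |
| 24 | 15 | 3 | 39/48 = 81.3%, in | B = 62.5%, out |
| 24 | 24 | 2 | 48/48 = 100%, in | out on setting |
| 19 | 19 | 3 | 38/48 = 79.2%, out | in by week count, out by percentage |

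The last row shows the SAP disagreeing with itself as well as with the protocol.

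**3. How far the rules can diverge.** Each unit can have 0 to 24 weeks of use. The protocol average needs A + B of at least 39 (0.80 × 48 = 38.4). That leaves 10 + 9 + … + 1 = 55 ordered combinations. Ignoring the setting condition:

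- with at least 19 weeks on each unit, 6 × 6 = 36 combinations meet the SAP count; removing 19/19, which fails the protocol, leaves 35 of the 55;
- with a true more-than-80% on each unit, 5 × 5 = 25 of the 55 remain.

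So 20 or 30 of the 55 combinations that pass the protocol fail the SAP. These are counts of possible patterns, not a forecast of participants.

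**4. One-unit homes.** Both definitions refer to both units. A home with one unit has no second unit to average or to test. Read literally, it qualifies under neither document. The documents do not say how many such homes there are.

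**5. What the survey measures.** A Yes in all 24 weeks scores 24/24 = 100%, whatever the hours of use. A week has 168 hours:

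- 1 hour a week: 1/168 = 0.6% of the time;
- 24 hours a week: 24/168 = 14.3%;
- two nights a week: at most 2/7 = 28.6%;
- continuous use: 168/168 = 100%.

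All four score the same. The kWh percentage could separate them, but SAP 4.2 gives no cut-off on it and no rule for when meter and survey disagree.

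**The case against.** Several points on the other side are fair. The SAP's setting condition is not a new idea: Protocol 6.1.1 already describes the intervention as continuous running at level 3. Caregiver report is a deliberate choice, and both documents explain it: some homes lack outlets that take the meter, and power interruptions alter its settings. SAP 4.2 does name the meters, the survey also records the usual setting, and SAP 3.7 adds an analysis limited to weeks with data. The family running its units two nights a week is hypothetical, and nothing in the documents shows how common that would be.

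These points limit the criticism but leave the differing rules, the 79.2% figure and the missing combination rule in place.

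A reader might also infer three stronger things that the documents do not support:

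- **That the SAP excludes every one-unit home.** No such exclusion is stated. It follows only from a literal reading of the words about both units, and the protocol uses the same words. The gap belongs to both documents.
- **That adherence cannot be measured at all.** It can be measured as the proportion of weeks with reported use, and quantitatively where meters work. What the survey cannot show is share of time within a week.
- **That the main result is in doubt.** It is not, because intention-to-treat is the primary set in both documents.

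**Conclusion.** The concern holds. The per-protocol set has two definitions that differ in averaging rule and setting condition, with no change recorded in SAP section 7. The SAP's week count falls one week short of its own threshold (79.2% at 19 weeks; 83.3% at 20). One-unit homes are unclassified in both documents. The primary compliance measure counts weeks with any reported use, and the meters have no stated part in deciding membership.

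The effect is confined to the separate per-protocol analysis. How many participants would change sets cannot be calculated, because the documents give neither the number of one-unit homes nor any distribution of use. The comparison of the two rules assumes that time is counted in weeks for both. The difference in setting condition does not depend on that assumption.

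**What to change.** Before unblinded analysis:

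1. Put one definition in Protocol 9.3 and SAP 3.7 and 4.2. Reconcile whether use is averaged or tested unit by unit and whether a setting condition applies, and record the change with its reason in SAP section 7.
2. Apply the threshold to each unit actually installed, so that a one-unit home is judged on its one unit.
3. Correct the week count to at least 20 of 24, or restate the percentage so that it agrees with 19.
4. Describe the survey measure as the proportion of weeks with reported use. State how weeks without a survey count in the main definition, and keep the available-weeks version as the additional analysis.
5. Add a sensitivity per-protocol set requiring observed over predicted kWh above 80%, where usable readings exist.

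The cost is wording in two documents and one extra analysis on data already being collected. The kWh set would cover only homes with three-prong outlets and readings not disrupted by power interruptions, so caregiver report should remain the primary compliance measure.
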